5.2. Masking

Complete masking is impossible due to the functioning nature of the Test lens. The Control lens will be over-labeled to mask the identity since the Control lens may be the subject's habitual lens by chance. Therefore, the study is partially-subject masked (Control lens only).

Under normal circumstances, the mask should not be broken until all subjects have completed the study and the database is finalized. Otherwise, the mask should be broken only if specific emergency treatment/course of action would be dictated by knowing the treatment status of the subject. In such cases, the investigator may in an emergency contact the medical monitor. In the event the mask is broken, the sponsor must be notified before the mask is broken. The date, time, and reason for the unmasking must be documented in the source document. The investigator is also advised not to reveal the study treatment assignment to the study site or sponsor personnel.

Subjects who have had their treatment assignment unmasked are expected to return for all remaining scheduled evaluations. Subjects who are discontinued may be replaced.

If the test article is randomized, the order will be based on the randomization scheme assigned to the study site. The study site will follow the randomization scheme provided and will complete enrollment according to the randomization list and will not pre-select or assign subjects.

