5.3. Procedures for Maintaining and Breaking the Masking

The test articles mask shall not be broken unless information concerning the lens type is necessary for the urgent medical treatment of a subject. The Sponsor must be notified before the mask is broken.

When dispensing test articles, the following steps should be followed to maintain randomization codes:

1. Investigator or designee (documented on the Delegation Log) will consult the lens fitting schedule/randomization scheme to obtain the test article assignment for that subject prior to dispensing
2. Investigator or designee will record the subject's number on the appropriate line of the randomization scheme
3. Investigator or designee will pull the appropriate test articles from the study supply. All test articles that are opened, whether dispensed (placed/fit on eye or dispensed outside the clinical site) or not, must be recorded on the Test Article Accountability Log in the "Dispensed" section

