7.2. Detailed Study Procedures

VISIT 1

Note that the subject must be wearing their habitual soft contact lenses into Visit 1.

Visit 1: Screening			
Step	Procedure	Details	
1.1	Statement of Informed Consent	Each subject must read, understand, and sign the Statement of Informed Consent before being enrolled into the study. The Principal Investigator or his/her designee conducting the informed consent discussion must also sign the consent form. Note: The subject must be provided a signed copy of this document.	
1.2	Demographics	Record the subject's date of birth, gender, race and ethnicity.	
1.3	Medical History and Concomitant Medications	Questions regarding the subjects' medical history and concomitant medications.	
1.4	Habitual Lenses	Questions regarding the subject's habitual lens type and parameters.	

Visit 1: Screening			
Step	Procedure	Details	
1.5	Eligibility after Screening	All responses to Screening Inclusion Criteria questions must be answered "yes" and all responses to Exclusion Criteria must be answered "no" for the subject to be considered eligible.	

Visit 1: Baseline			
Step	Procedure	Details	
1.6	Baseline Questionnaires	The subject will respond to the following questionnaires: 1. CLUE Baseline Questionnaire 2. GSI Background Questionnaire	
1.7	Other Questionnaires	The subject will respond to additional questionnaires: 1. Activity History	
1.8	Entrance Visual Acuity	Record the distance Snellen visual acuity (OD, OS, and OU) to the nearest letter with their habitual contact lens correction in place. Subjects must read the smallest line until at least 50% of the letters are read incorrectly.	
1.9	Remove Habitual Lens	The subject's habitual lenses will be removed and stored in their own lens case. If they forgot to bring their lens case, one will be provided to them.	
1.10	Slit Lamp Findings	FDA Slit Lamp Classification Scale [REDACTED] [REDACTED] will be used to grade the findings and will be used to determine eligibility. Record only whole numbers. If any of these slit lamp findings are Grade 3 or higher, the subject is ineligible to continue but may return at a later date to complete another Baseline. If after a total of 2 attempts the subject is deemed ineligible, then complete the Final Evaluation. Limbal and Bulbar Conjunctival Hyperemia findings [REDACTED] using the 0.5 increment scale, and Corneal Staining Assessment	

Visit 1: Baseline			
Step	Procedure	Details	

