1.23	Continuance	
For the subject to continue in the study, they must meet all three of the following criteria:
 
 1. Snellen visual acuity is 20/30 or better OD and OS 2. The lens fit is acceptable OD and OS 3. Investigator approval. If the Investigator does not approve the dispensing of the first study lens, then the study is terminated for that subject. 	
1.24	Dispense	
The lenses will be dispensed for 13-15 days
 
 1. The subjects should wear their lenses similar to the inclusion criteria: ≥ 6 hours per day, ≥ 5 days per week. 2. The lenses will be worn as daily wear only. 3. All subjects will be provided Opti-Free® PureMoist® to be used in a rub regime. 	

Visit 1: Treatment 1 Lens Fitting			
Step	Procedure	Details	
		
4. Preservative-free rewetting drops are permitted if needed.
 
5. A patient instruction booklet will be provided.
 
6. The lenses must be stored in the supplied case out of direct sunlight.
 
Note 1: In the event a lens is lost or damaged, the subject will return to the investigator site for replacement (extra lenses cannot be given at the dispensing visit).
 
Note 2: The subject's habitual contact lenses cannot be worn at any time during the study.
 
Note 3: The subject must be instructed: At each of your follow-up visits in this research study, we'll ask about the lenses you're wearing. These questions will address lens comfort and vision, including color perception in different lighting conditions and the ability to see comfortably in bright light
	

VISIT 2

The follow-up will occur 13-15 days following Visit 2. The subjects must enter the visit wearing their study contact lenses.

Visit 2: Treatment 1 Follow-Up			
Step	Procedure	Details	
2.1.	Adverse Events and Concomitant Medications Review	
Review the subject's concomitant medications and record any changes from the previous study visit.
 
Record any adverse events or medical history changes from the previous study visit.
	
2.2.	Wearing Time	Record the average wearing time and comfortable wearing time.	
2.3.	Compliance	Confirm compliance with the prescribed wear schedule. Outdoor and total hours will be asked.	
2.4.	Subject Reported Ocular Symptoms	Subjects will respond to a verbal open-ended symptoms questionnaire.	

Visit 2: Treatment 1 Follow-Up			
Step	Procedure	Details	

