2.5.	Follow-Up Questionnaire	Subjects will respond to the following questionnaires: 1. CLUE Follow-up 2. GSI Product Performance	
2.6.	Visual Acuity	Record the distance Snellen visual acuity with the contact lenses (OD, OS, and OU) to the nearest letter. Subjects must read the smallest line until at least 50% of the letters are read incorrectly.	
2.7.	Quick Contrast Sensitivity	████████ only. Perform the 4 m contrast sensitivity test once OD and OS using the 25-item methodology while wearing the study lenses.	
2.8.	logMAR (ETDRS) Visual Acuity	Perform 4 m distance ETDRS LogMAR visual acuity test OD and OS under the following conditions: 1. Bright room illumination / low contrast charts a. Room illumination >400 lux b. Chart luminance 120-200 cd/m ² c. One low contrast chart per eye. 1) OD: chart LC-1 2) OS: chart LC-2 2. Low room illumination / high contrast charts a. Room illumination <2.5 lux b. Chart luminance 2.0-5.0 cd/m ² c. One high contrast chart per eye. 1) OD: chart HC-1 2) OS: chart HC-2	████████ ████████
2.9.	Subjective Lens Fit Assessment	Subjective Assessment of the Lens Fit. If the fit is graded as unacceptable based on the criteria below, then the subject is discontinued from the study and will not be replaced. 1. Limbal exposure in any gaze 2. Edge lift 3. Insufficient and/or excessive movement in all three movement categories	

Visit 2: Treatment 1 Follow-Up			
Step	Procedure	Details	
2.10.	Surface Deposits	Record any front and back surface lens deposits.	
2.11.	Lens Removal & Storage	Both lenses will be removed and stored wet in a labeled container with Opti-Free® PureMoist®. The lenses can be stored refrigerated or frozen prior to shipment back to the Sponsor. Lenses will be stored at JJVC for 45 days after LSLV for laboratory testing (Section 7.4).	
2.12.	Slit Lamp Findings	
Slit Lamp Classification Scale [REDACTED] will be used to grade the findings. Record only whole numbers. Limbal and Bulbar Conjunctival Hyperemia findings [REDACTED] [REDACTED] and Corneal Staining Assessment [REDACTED] [REDACTED] will be emphasized using a more detailed scale.
 
Note: Findings must be grade 2 or less as graded on the FDA scale [REDACTED] to continue onto Trial Period 2. If the subject is not eligible, they must be followed as an adverse event. Once resolved, the subject is terminated from the study. Adverse events must be reported to the JJVC monitors immediately.
	[REDACTED] [REDACTED] [REDACTED]

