2.23.	Dispense	
The lenses will be dispensed for 13-15 days.
 
 1. The subjects should wear their lenses similar to the inclusion criteria: ≥ 6 hours per day, ≥ 5 days per week. 2. The lenses will be worn as daily wear only. 3. All subjects will be provided Opti-Free® PureMoist® to be used in a rub regime. 4. Preservative-free rewetting drops are permitted if needed. 5. The lenses must be stored in the supplied case out of direct sunlight. 
Note 1: In the event a lens is lost or damaged, the subject will return to the investigator site for replacement (extra lenses cannot be given at the dispensing visit).
 
Note 2: The subject's habitual contact lenses cannot be worn at any time during the study.
	

VISIT 3

The follow-up will occur 13-15 days after the dispensing of the second study lenses. The subjects must enter the visit wearing their study contact lenses.

Visit 3: Treatment 2 Follow-Up			
Step	Procedure	Details	
3.1.	Adverse Events and Concomitant Medications Review	Review the subject's concomitant medications and record any changes from the previous study visit.	

Visit 3: Treatment 2 Follow-Up			
Step	Procedure	Details	
		Record any adverse events or medical history changes from the previous study visit.	
3.2.	Wearing Time	Record the average wearing time and comfortable wearing time.	
3.3.	Compliance	Confirm compliance with the prescribed wear schedule. Outdoor and total hours will be asked.	
3.4.	Subject Reported Ocular Symptoms	Subjects will respond to a verbal open-ended symptoms questionnaire.	
3.5.	Follow-Up Questionnaire	Subjects will respond to the following questionnaires: 1. CLUE Follow-up 2. GSI Product Performance	
3.6.	Lens Preferences	Subjects will respond to the preference questionnaire comparing study lens 1 and study lens 2.	
3.7.	Visual Acuity	Record the distance Snellen visual acuity with the contact lenses (OD, OS, and OU) to the nearest letter. Subjects must read the smallest line until at least 50% of the letters are read incorrectly.	
3.8.	Quick Contrast Sensitivity	Site 1036 only. Perform the 4 m contrast sensitivity test once OD and OS using the 25-item methodology while wearing the study lenses.	

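### At each follow-up visit the CLUE and other questionnaires come after a staff interview about comfort and symptoms, by someone who may know the lens; moving them first would close that route for bias

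*Protocol*

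**What the plan says.** Protocol Section 7.2 gives the same opening order at Visits 2, 3 and 4:

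- x.1: review of medications and adverse events ("Record any adverse events or medical history changes from the previous study visit")
- x.2: "Record the average wearing time and comfortable wearing time"
- x.3: wear-schedule compliance, with outdoor and total hours asked
- x.4: "Subjects will respond to a verbal open-ended symptoms questionnaire"
- x.5: "Subjects will respond to the following questionnaires: 1. CLUE Follow-up", together with the GSI product performance questionnaire
- 3.6 (Visit 3 only): lens preference

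Acuity, contrast sensitivity, fit, deposits and slit lamp come later in the visit.

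On masking, Protocol Section 5.2 states "Complete masking is impossible due to the functioning nature of the Test lens" and concludes "Therefore, the study is partially-subject masked (Control lens only". Under Section 5.3 the investigator or designee "will consult the lens fitting schedule/randomization scheme to obtain the test article assignment for that subject prior to dispensing". Section 5.2 also advises the investigator not to disclose the assignment to site or sponsor personnel. No visible text names who carries out steps x.1 to x.4, or requires that person to be unaware of the lens.

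**The concern.** CLUE overall comfort and the single CLUE item on vision in bright light are primary endpoints. CLUE vision, CLUE handling and vision indoors carry secondary hypotheses. Just before giving these ratings, the subject talks with site staff about comfortable hours of wear, time outdoors and symptoms. If the interviewer knows the lens and, without meaning to, probes or responds differently for Test and Control, the ratings can move differently for the two lenses. In a non-inferiority comparison a shift towards Test makes a false claim more likely, and a shift away from Test costs power. Neither could be detected or corrected afterwards from the data the plan collects.

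**Working it through.** **1. Step order.** CLUE is step 2.5, 3.5 and 4.5, after four steps of staff contact each time. The order is identical at all three visits, so it applies to every post-baseline CLUE score.

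**2. What the crossover removes.** Let the interview shift a rating by a when Control is worn and by a + b when Test is worn. With Lens = 0 for Control and 1 for Test, as both documents code it, the shift in any period is a + b·Lens.

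- The common part a goes into the intercept and cancels from the comparison.
- The differential part b has exactly the same design column as the lens effect, so the model estimates β1 + b.
- Period, sequence and carryover terms do not separate the two.
- For the ordinal items, a differential shift c on the logit scale multiplies the odds ratio by exp(c) in the same way.

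Only b matters, and the documents give no value for it.

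**3. Illustration for CLUE comfort.** No figure in the plan depends on step order, so there is none to reproduce for this point. To show the scale I used:

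- the comfort covariance matrix (Protocol Section 14.2, SAP Section 8.4);
- sequences Test/Control/Control and Control/Test/Test, with 105/2 = 52.5 subjects each;
- the -5 margin and the 0.975 decision rule (Protocol Section 14.5, SAP Section 11.1).

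The generalised least squares variance is Var(β1) = lens entry of [Σ_s n_s X_s' Σ^-1 X_s]^-1. This gives SE = 1.95 with lens as the only effect and 1.98 with period, sequence and carryover added. As a check on the inputs, the same formula at N = 30 gives SE = 3.65. Power at a true difference of +5 is then about 86% with one-sided alpha 0.05, close to the plan's 87%. (Under the 0.975 rule it is 75% to 77%; that is a separate matter.)

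Non-inferiority is declared when (estimate + 5)/SE exceeds t(0.975, 103) = 1.983. At a true difference of -5 with shift b, the chance is P(T > 1.983 - b/SE). For b = 1: 1/1.952 = 0.512, 1.983 - 0.512 = 1.471, giving 7.2%. At a true difference of 0 the chance comes from the noncentral t with noncentrality (5 + b)/SE.

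| Assumed b (points; + favours Test) | Declared non-inferior, true difference -5 | Declared non-inferior, true difference 0 |
|---|---|---|
| -3 | not computed | 17% |
| -2 | not computed | 33% |
| -1 | not computed | 53% |
| 0 | 2.5% | 72% |
| +1 | 7.2% | 86% |
| +2 | 17.0% | 94% |
| +3 | 32.8% | 98% |

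At the planning difference of +5, power is 99.9% with b = 0 and still 94% with b = -3. On the margin itself, 1/5 = 20% and 2/5 = 40%, so a 1- or 2-point shift is that share of the 5 points.

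These are large-sample approximations to the Bayesian model with vague priors. They leave out the baseline covariate and the random site effect.

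**The case against.** Several counter-arguments have force.

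- **The interviewer's knowledge is inferred.** A reader might conclude that staff who know the lens conduct the interview. The documents do not say so. They describe a lookup by the investigator or designee and advise against passing the assignment on, and a coordinator or technician may perform some visit tasks. What stands is that no separation of roles is set up, so the interviewer may know.
- **The prompts are mostly neutral.** Times and hours are recorded and the symptom question is open-ended, which leaves limited room to lead. The room is not zero.
- **The redactions.** The Appendix D procedures for patient-reported outcomes and for subject-reported symptoms are blacked out. They may contain rules on self-completion or interviewer neutrality, so the plan cannot be faulted for lacking such rules. The visible visit steps still put CLUE fifth.
- **Larger influences remain.** The Test lens cannot be fully masked, so subjects may recognise it. At first dispensing (step 1.24, Note 3) every subject is also told to expect questions on comfort and on seeing in bright light. Reordering removes only what the interview adds.
- **A safeguard already exists.** The questionnaires precede all the eye and lens examinations, so examination results cannot colour the ratings.

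A reader might also infer a bias from the baseline visit, where "The subject will respond to the following questionnaires: 1. CLUE Baseline Questionnaire" (step 1.6) comes before the symptom interview (step 1.20). That does not follow. The baseline score is a single value per subject, taken on habitual lenses before lens assignment (step 1.15), and it too follows staff questions (steps 1.3 and 1.4). It cannot bias the Test-Control contrast, and the bright-light model has no baseline term.

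**Conclusion.** The point holds as a cheap improvement to procedure. It is not an error in the plan and not evidence that results will be biased. The step order is certain. The possibility of a lens-differential influence rests on the absence of any described staff masking and on the assignment lookup at the site. If present, such an influence would be fully confounded with the lens effect for the two primary and three secondary patient-reported endpoints (taking the vision indoors item to be collected at step x.5).

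The size and direction are unknown. The 1- to 3-point shifts above are assumptions with no anchor in the documents. They show only that a small differential shift matters if the true comfort difference lies between the margin and zero, and matters little if the planning difference of +5 is right. The stake is therefore mainly the credibility of a non-inferiority claim.

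Reordering is also not the only remedy: an interviewer without access to the randomization scheme would serve the same purpose.

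**What to change.** In Protocol Section 7.2, make steps 2.5, 3.5 to 3.6 and 4.5 (CLUE, product performance and, at Visit 3, lens preference) the first step on arrival. Subjects would complete them on their own with the study lenses in place, before steps x.1 to x.4. Content stays the same, and subjects already have to arrive wearing the lenses. If the Appendix D procedures already set administration rules, cross-refer to them so that the visit steps and those rules agree.

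The cost is an amendment to Section 7.2 with the usual ethics review, a change to the EDC visit flow, and a short delay to the adverse event review within each follow-up visit, which the clinical team should confirm is acceptable. No extra procedures or subjects are needed. The report should still acknowledge that subjects may recognise the Test lens, because this change does not address that.

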7.3. Unscheduled Visits

If, during the investigation, a subject requires an unscheduled visit to the clinical site, the following information will be collected at a minimum:

- Chief complaint prompting the visit. If the reason is an adverse event, the applicable eCRF for the adverse event must be completed and subject record completed as appropriate
- Date and time of the visit and all procedures completed at the unscheduled visit
- Review of adverse event and concomitant medications
- Documentation of any test article dispensed or collected from the subject, if applicable
- Slit lamp findings (using the Slit Lamp Classification Scale)

If the Investigator withdraws a subject from the study, the final study visit case report forms must be completed indicating the reason(s) why the subject was withdrawn. The subject record must be completed documenting the date and primary reason for withdrawal and the study CRA notified.

Any ocular and non-ocular Adverse Events that are ongoing at the time of the study visit will be followed by the Investigator, within licensure, until they have resolved, returned to pre-treatment status, stabilized, or been satisfactorily explained. If further treatment i.e., beyond licensure is required, the subject will be referred to the appropriate health care provider.

The following information will be collected during an unscheduled visit.

Step	Procedure	Details	
U.1	Chief Complaints	Record the subject's chief complaints for reasons for the unscheduled visit	
U.2	Change of Medical History and Concomitant Medications	Questions regarding the change of subjects' medical history and concomitant medications.	
U.3	Entrance VA	Record the entrance distance visual acuity (OD, OS and OU) to the nearest letter.	
U.4	Subjective Sphero-cylindrical Refraction	The investigator will complete a subjective refraction (sphere and cylinder) and record the resultant distance visual acuity OD, OS, and OU to the nearest letter.	
U.5	Slit Lamp Biomicroscopy	FDA Slit Lamp Classification Scale will be used to grade the findings. If no slit lamp finding is noted on the EDC form it is considered as a zero "0" Grade for all observations listed. After the slit lamp examination, at the discretion of the Investigator, rinse the subject's eyes thoroughly with preservative-free saline.	
U.6	Dispensing (if applicable)	Additional lenses may be dispensed if one is lost or torn during the wearing period.	
U.7	Exit Visual Acuity	Record the subject's exit distance visual acuity (OD, OS and OU) to the nearest letter.	

7.4. Laboratory Procedures

The optical bench will be used to measure the light transmission characteristics for all worn Test lenses. The findings are for internal information only and will not be part of the final report.

8. SUBJECTS COMPLETION/WITHDRAWAL

8.1. Completion Criteria

Subjects are considered to have completed the study if they:

- provided informed consent
- completed all scheduled visits

8.2. Withdrawal/Discontinuation from the Study

A subject will be withdrawn from the study for any of the following reasons:

- Subject death during the study period
- Subject withdrawal of consent
- Subject not compliant to protocol (e.g. Subject more than 2 days out of visit window).
- Subject lost to follow-up
- Subject no longer meets eligibility criteria (e.g. the subject becomes pregnant)
- Subject develops significant or serious adverse events causing discontinuation of study lens wear (subjects missing more than 2 days of missed lens wear within a period 1 of week should be discontinued)
- Subjects who have experienced a Corneal Infiltrative Event (CIE)
- Investigator's clinical judgment regarding the subject safety reasons (that it is in the best interest of the subject to stop treatment)
- Subject missed any scheduled study visits
- Subject not compliant with study lens wear schedule
- Subject not successfully dispensed due to lack of efficacy and safety including poor vision, poor comfort or unacceptable fit

For discontinued subjects, the Investigator will:

- Complete the current visit (scheduled or unscheduled)
- Complete the Final Evaluation, indicating the reason that the subject was discontinued from the study
- Record the spherocylindrical refraction with best corrected distance visual acuity
- Collect used test article(s) (worn or brought to the visit) from the subject and discard them, unless otherwise stated in Section 7.2.
- Collect all unused test article(s) from the subject

Investigator will discuss with sponsor before enrolling any additional subjects if a subject discontinues from the study prematurely.

In cases where a subject is lost to follow-up, every possible effort must be made to contact the subject and determine the reason for discontinuation/withdrawal. The measures taken to

follow up must be documented including two written attempts and a certified letter (or equivalent) as the final attempt.

